### 5.5.2 Skin Reactions

Recommendations for management of photosensitivity reactions are outlined below in [Table 5-2](#).

Photosensitivity was reported in patients treated with Rova-T including severe events.

Photosensitivity reactions may occur hours to days after sun exposure. The median time to onset was 30 days (range 1 to 247 days). Patients should be advised to avoid direct and indirect sun exposure as much as possible during Rova-T treatment and for 30 days after the last dose. If unavoidable, patients should wear protective clothing and sunglasses, and use a broad-spectrum sunscreen and lip balm (SPF 30 or greater). 31 – 90 days after last dose, the patient may resume outdoor activities with appropriate sun protection including broad brimmed hat, protective clothing and sunscreen SPF 30 or higher. Skin reactions should be evaluated promptly and treated with topical or systemic steroids as indicated (refer to [Table 5-2](#)). Rova-T dose should be delayed, reduced or discontinued as necessary (refer to [Table 5-1](#))

All cutaneous reactions which develop during treatment warrant prompt evaluation. Skin toxicity with rovalpituzumab tesirine may consist of photosensitivity but possibly other reactions such as palmar-plantar erythrodysesthesia or erythema multiforme. As such, development of a cutaneous reaction during treatment warrants prompt evaluation by the Investigator or designee:

- If clinically consistent with photosensitivity, the AE should be reported as such (using medically accurate and descriptive AE terminology), and managed as described below in [Table 5-2](#).

- For clinically more severe cases of photosensitivity or if clinically not consistent with photosensitivity, photodocumentation to facilitate later review by the Sponsor or designee may occur.
  - Formal evaluation by a dermatologist, including possible skin biopsy to rule out alternative etiologies, such as erythema multiforme which may warrant discontinuation of study drug, and to facilitate the most appropriate terminology for AE reporting, is recommended.
  - Photodocumentation of skin toxicity, if available, may be requested by the TAMD. The investigative site will take measures to protect the identity of the patient. These measures include taking the photograph very close to the affected skin region to exclude facial features, or if facial features cannot be excluded due to the location of the skin reaction, covering identifying features (such as the eyes) with a black rectangle.

All events of cutaneous toxicity should be monitored until resolution or return to baseline.

**Table 5-2 Recommended Management of Photosensitivity**

CTCAE v4.03		Treatment Recommendations	Dose Modifications
Grade 1	Painless erythema and erythema covering <10% BSA	Low-potency topical steroid (face) High-potency topical steroid (body)	–
Grade 2	Tender erythema covering 10–30% BSA	Low-potency topical steroid (face) High-potency topical steroid (body) Nonsteroidal anti-inflammatory agents orally as needed	–
Grade 3	Erythema covering >30% BSA and erythema with blistering; photosensitivity; oral corticosteroid therapy indicated; pain control indicated (e.g., narcotics or NSAIDs)	Low-potency topical steroid (face) High-potency topical steroid (body) Prednisone 0.5 mg/kg × 7 days	Reduce dose
Grade 4	Life-threatening consequences; urgent intervention indicated	Low-potency topical steroid (face) High-potency topical steroid (body) Prednisone 0.5 mg/kg × 7 days Hospitalization	Reduce dose

BSA = body surface area; CTCAE = Common Terminology Criteria for Adverse Events; NSAIDs = non-steroidal anti-inflammatory drug.

### 5.5.3 Potential Drug-Induced Liver Injury

Wherever possible, timely confirmation of initial liver-related laboratory abnormalities should occur prior to the reporting of a potential drug-induced liver injury (DILI) event. All occurrences of potential DILIs, meeting the defined criteria, must be reported as SAEs.

Potential drug-induced liver injury is defined as:

- ALT or AST elevation  $>3\times$  ULN; *and*
- Concurrent total bilirubin  $>2\times$  ULN, without initial findings of cholestasis (elevated serum alkaline phosphatase), *and*
- No other immediately apparent possible causes of aminotransferase (AT) elevation and hyperbilirubinemia, including, but not limited to, viral hepatitis, pre-existing chronic or acute liver disease or tumor(s), or the administration of other drug(s) known to be hepatotoxic

In general, an increase of AT to  $>3\times$  ULN should be followed by repeat testing within 48–72 hours of all four of the usual measures (ALT, AST, alkaline phosphatase, total bilirubin) to confirm the abnormalities and to determine if they are increasing or decreasing. Inquiry regarding symptoms should also be made (e.g., fatigue, nausea, vomiting, right upper quadrant pain or tenderness, fever, rash). Subjects may be retested locally, but normal laboratory ranges should be recorded and results made to the Investigator immediately. All data must be recorded in the CRF. If symptoms persist or repeat testing shows AT  $>3\times$  ULN for subjects with normal baseline measures or 2-fold increases above baseline values for subjects with elevated values before drug exposure, close observation should be initiated. If close monitoring is not possible, study drug should be discontinued.

Close observation includes:

- Repeating liver enzyme and serum bilirubin tests 2 or 3 times weekly. Frequency of retesting can decrease to once a week or less if abnormalities stabilize or the trial drug has been discontinued and the subject is asymptomatic.
- Obtaining a more detailed history of symptoms and prior or concurrent diseases
- Obtaining a history of concomitant drug use (including nonprescription medications and herbal and dietary supplement preparations), alcohol use, recreational drug use, and special diets
- Ruling out acute viral hepatitis types A, B, C, D, and E; autoimmune or alcoholic hepatitis; non-alcoholic steatohepatitis (NASH); hypoxic/ischemic hepatopathy; and biliary tract disease
- Obtaining a history of exposure to environmental chemical agents
- Obtaining additional tests to evaluate liver function, as appropriate (e.g., international normalized ratio [INR], direct bilirubin)
- Considering gastroenterology or hepatology consultations

Discontinuation of study drug should be considered if potential DILI is suspected and:

- ALT or AST  $>8\times$  ULN
- ALT or AST  $>5\times$  ULN for more than 2 weeks

- ALT or AST  $>3\times$  ULN and (TBL  $>2\times$  ULN or INR  $>1.5$ )
- ALT or AST  $>3\times$  ULN with the appearance of fatigue, nausea, vomiting, right upper quadrant pain or tenderness, fever, rash, and/or eosinophilia

All subjects showing possible DILI should be followed until all abnormalities return to normal or to the baseline state.

#### **5.5.4 Monitoring and Management of Edema**

- The majority of the edema events with rovalpituzumab tesirine have been reported as low grade 1 or 2 (mild or moderate); however, a small number of fatal events of generalized edema have been reported with rovalpituzumab tesirine. Physical exams and monitoring of weight gain and signs or symptoms of fluid retention should be conducted during treatment.
- Consistent with institutional guidelines or standard practice, the use of diuretics with or without albumin may be considered in subjects with clinically significant edema and hypoalbuminemia. The selection and use of diuretics in subjects should be based on individual clinical characteristics and include monitoring of electrolyte status and signs or symptoms of intravascular volume depletion such as hypotension and impaired renal function.
- Systemic corticosteroids, when initiated promptly, have been reported to be beneficial in some prior cases.

#### **5.5.5 Monitoring and Management of Pneumonitis:**

- Pneumonitis has been infrequently reported with rovalpituzumab tesirine but has resulted in fatal outcomes. Although the causal role of rovalpituzumab tesirine could not be ruled out, the reports of pneumonitis had one or more confounders including underlying pulmonary disease/cancer, prior thoracic radiation, prior cytotoxic chemotherapy or clinical evidence suggestive of an alternative diagnosis including pneumonia.
- Heavily pretreated SCLC patients and patients with a history of pneumonitis may be at increased risk, and careful monitoring for signs and symptoms of pneumonitis is important. The risk of pneumonitis is increased with prior radiation to lung.
- In general signs and symptoms coinciding with or preceding pneumonitis may include new or worsening cough, chest pain and/or shortness of breath, fever, and radiographic changes (reticular markings, ground glass opacities). Protocol defined disease assessments provide for the opportunity for on study pulmonary monitoring for detection of pneumonitis. The protocol allows for additional imaging per physician discretion for signs and symptoms of pulmonary toxicity.

- The diagnosis of drug induced pneumonitis is one of exclusion. Other etiologies including infection, which is a common cause of pulmonary infiltrates with clinical and radiographic appearance similar to drug-induced pneumonitis, need to be carefully considered and excluded before the diagnosis of drug induced pneumonitis can be established.
- If pneumonitis is suspected, close monitoring including additional laboratory and imaging investigation per institutional guidelines may be necessary. Systemic corticosteroids may be beneficial for rapidly progressive or more severe pneumonitis.

For Grade 1 pneumonitis, monitor closely. For dose modification, please see Table 5-1 of the protocol.

### **5.6 Treatment Compliance**

Study drug administration must be performed by study site staff and documented in source documents and the CRF.

### 6.2 Screening Visit (Days -15 to -1)

- Informed consent – omitted for retreatment subjects
- Demographics ([Section 7.1](#)) – omitted for retreatment subjects
- Study eligibility – according to Inclusion/Exclusion Criteria ([Section 4](#))
- Medical and surgical history ([Section 7.1](#)) – omitted for retreatment subjects
- Malignancy history ([Section 7.1](#)) – omitted for retreatment subjects
- Prior anticancer treatments ([Section 7.1](#)) – omitted for retreatment subjects
- Physical examination ([Section 7.2.1](#))
- Vital signs ([Section 7.2.2](#))
- Height ([Section 7.2.2](#))
- PRO questionnaires EORTC QLQ-C30 and EQ-5D-5L – for subjects in Part B of the study only ([Section 7.3.2](#))
- Complete blood count ([Section 7.2.3](#))
- Serum chemistries ([Section 7.2.3](#))
- Coagulation tests ([Section 7.2.3](#))
- Urinalysis ([Section 7.2.3](#))
- Hepatitis B and C tests ([Section 7.2.3](#)) – omitted for retreatment subjects
- Pregnancy test ([Section 7.2.9](#)) – for women of childbearing potential
- Electrocardiogram (ECG) in triplicate ([Section 7.2.4](#))
- ECHO – the screening ECHO should be done any time before the first dose of study drug.

- ECOG performance status ([Appendix 13.3](#))
- Disease assessment consisting of CT scans of the chest, abdomen, and pelvis (and neck if indicated; [Section 7.3](#)) – may be omitted for retreatment subjects if recent scans demonstrating PD are within 2 weeks of study drug dosing (Day 1 of the first cycle of retreatment).
- MRI of the brain – may be omitted for retreatment subjects if recent scans demonstrating PD are within 2 weeks of study drug dosing (Day 1 of the first cycle of retreatment). CT of the brain with intravenous contrast may be substituted at the discretion of the Investigator.
- Tumor tissue – Collected upon an archived or fresh specimen ([Section 7.5.1](#)). Previously obtained DLL3 tumor expression results may be substituted if assessed previously via central immunohistochemistry assessment – omitted for retreatment subjects.
- Prostate cancer subjects only:
  - Serum total testosterone – omitted for retreatment subjects
  - 99mTc Bone Scintigraphy ([Section 7.3](#)) – may be omitted at initial screening if scans have been performed within 2 weeks. May be omitted for retreatment subjects if recent scans demonstrating PD are within 2 weeks of study drug dosing (Day 1 of the first cycle of retreatment).

### 6.3 Treatment Period

The treatment period for subjects in Schedule Q6wk is Day 1 to 42 of each 6-week cycle.

#### 6.3.1 Day -1 (Day before Dosing)

- Subjects will take dexamethasone 8 mg PO twice a day

#### 6.3.2 Day 1 (±2 Days)

If screening visit activities occur within 1 day prior to Cycle 1, Day 1, the following pre-dose assessments do not need to be repeated at the Cycle 1, Day 1 visit: physical examination, ECOG performance status, and local safety labs (CBC, chemistries, coagulation tests, urinalysis, pregnancy test; if obtained within 1 calendar day).

Day 1 procedures may be performed within 1 calendar day prior to dosing of study drug. Results from local clinical laboratory tests (at least CBC with differential and serum chemistry panel) must be available prior to dose.

- Physical examination ([Section 7.2.1](#))
- Vital signs – within 30 minutes prior to the infusion, then post-infusion at 30 minutes after start of infusion (±10 minutes), 2 hour (±15 minutes) and 4 hour (±30 minutes; [Section 7.2.2](#))

- PRO questionnaires EORTC QLQ-C30 and EQ-5D-5L – for subjects in Part B of the study only; to occur at screening, Cycle 2 (Days 1 and 29), and EOT ([Section 7.3.2](#))
- CBC ([Section 7.2.3](#))
- Serum chemistries ([Section 7.2.3](#))
- Coagulation tests ([Section 7.2.3](#))
- Urinalysis ([Section 7.2.3](#))
- Pregnancy test ([Section 7.2.9](#)) – for women of childbearing potential
- ECG in triplicate – within 180 minutes prior to infusion, and then post-infusion at 30 minutes ( $\pm 10$  minutes; [Section 7.2.4](#))
- ECHO ([Section 7.2.5](#)) – The screening ECHO should be done any time before the first dose of study drug; all ECHOs after C1D1 should be conducted within 4 days before the next dosing.
- ECOG performance status ([Section 7.2.6](#))
- Fluid retention questionnaire ([Section 7.2.7](#))
- Blood sample for PK – Should be drawn within 30 minutes prior to the infusion, and then post-infusion at 30 minutes after start of infusion ( $\pm 10$  minutes). In Cycles 1 and 2, an additional sample will be taken at 6 hour ( $\pm 30$  minutes). The 6 hour PK sample is required for Cycles 1 and 2 only - omitted for retreatment subjects.
- Blood sample for ATA
- Blood inflammatory markers ([Section 7.5.2](#))
- Blood tumor markers ([Section 7.5.3](#))
- Soluble biomarkers ([Section 7.5.4](#))
- Circulating tumor cells (CTCs), collected at Cycle 1 Day 1. ([Section 7.5.5](#))
- Subjects will take dexamethasone 8 mg PO twice a day (the first dose of the day should be at least 30 minutes, but no more than 4 hours, prior to the rovalpituzumab tesirine dose)
- Administration of rovalpituzumab tesirine ([Section 5.1](#))

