### 2.4.4 Pharmacokinetics, Biomarker, and Pharmacodynamic Endpoints

- Specific PK parameters of rovalpituzumab tesirine (e.g., maximum concentration [ $C_{max}$ ], area under the curve [AUC])
- ATA against rovalpituzumab tesirine
- Tumor DLL3 expression
- Inflammatory markers (locally tested)
- Blood tumor markers
- Biomarkers, including soluble DLL3
- CTCs

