#### **5.2.3 Dosing**

The actual dose is based on the subject's actual body weight on C1D1 to the nearest kilogram, and administered according to the assigned dose. If the subject's actual weight at subsequent cycles is within 10% of the C1D1 weight, the dose will not be adjusted due to weight changes. Otherwise, the dose will be adjusted based on the actual body weight to the nearest kilogram at that cycle. Rovalpituzumab tesirine will be administered intravenously (IV) over 30 minutes (treatment window: 20 to 40 minutes) on Day 1 of each 6-week cycle.

Subjects must meet all of the following on each dosing day before receiving study drug:

- ANC  $\geq$ 1,000/ $\mu$ L
- Platelet count  $\geq$ 75,000/ $\mu$ L
- Resolution to Grade 0 or 1, or to baseline grade if pre-existing, of any clinically-significant AEs or laboratory abnormalities occurring during the previous cycle

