### 10.3.8 Pharmacokinetic and Pharmacodynamics Analyses

Data from the Pharmacokinetic-Evaluable Set will be used in the analysis of PK and Pharmacodynamics endpoints. The PK of rovalpituzumab tesirine will be estimated from concentration-time data using non-compartmental methods. The reporting of PK parameters will be determined based on the final parameter analysis on the available data. The PK parameters that may be assessed include, as appropriate:

- $C_{\max}$  Maximum plasma concentration
- AUC Area under the plasma concentration-time curve
- $T_{\max}$  Time of  $C_{\max}$
- $C_{\text{trough}}$  Plasma concentrations at trough
- $t_{1/2}$  (Apparent) terminal half-life
- CL Plasma clearance
- $V_{d\beta}$  Volume of distribution

The above parameters will be summarized by descriptive statistics.

The incidence and timing of ATA to study drug will be summarized by descriptive statistics. The possible effects of ATA on PK, efficacy and safety may be explored. Details will be provided in the SAP.

The five-number summary will be used to describe absolute and percent change from baseline in IHC, blood tumor markers (like NSE), soluble biomarkers (such as soluble DLL3) and circulating tumor cells. Regressions may be performed as appropriate. Exploratory analyses may be performed to evaluate a possible correlation between each of these endpoints and disease response and/or toxicities. Additional analyses may also be performed. Details will be provided in the SAP.

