### 13.2 Schedule of Day 1 Periodosing Assessments

Time Window	Predose		Dosing	Postdose		
	-	0		+2 Hours post SOI*	+4 Hours post SOI*	+6 Hours post SOI*
	-30 to 0 Minutes	-	+30 Minutes post SOI* ±10 Minutes	±15 Minutes	±30 Minutes	±30 Minutes
Rovalpituzumab Tesirine Administration		X				
Vital Signs 	X		X	X	X	
Electrocardiogram 	X		X			
Pharmacokinetic sample	X		X			X 

\*SOI = Start of infusion

- 1) Vital signs according to [Appendix 13.1](#).
- 2) ECG (in triplicate) according to [Appendix 13.1](#); up to 180 minutes predose.
- 3) The 6 hour PK sample is to be drawn Cycles 1 and 2 only – omitted for retreatment subjects.

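### The first post-dose PK sample is labelled post-infusion but timed from the start of a 20-to-40-minute infusion, so it can be drawn mid-infusion and miss the peak

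*Combined protocol and SAP*

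**What the plan says.** Section 5.2.3 states that the drug "will be administered intravenously (IV) over 30 minutes (treatment window: 20 to 40 minutes) on Day 1".

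Section 6.3.2 says of the Day 1 PK sample: "Should be drawn within 30 minutes prior to the infusion, and then post-infusion at 30 minutes after start of infusion", ±10 minutes. Appendix 13.2 repeats this as "30 Minutes post SOI* ±10 Minutes" and defines the abbreviation: "SOI = Start of infusion". The label says the infusion is over, but the clock runs from its start. Neither place requires the infusion to have ended before the draw.

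A further sample at 6 hours (±30 minutes) is taken in Cycles 1 and 2 only and is omitted in retreatment (6.3.2, 13.2). The Day 3, 8, 15 and 29 PK samples carry the same restriction (6.3.4, 6.3.5).

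Section 2.4.4 lists "Specific PK parameters of rovalpituzumab tesirine (e.g., maximum concentration" and AUC as examples of the PK endpoints. Section 10.3.8 says the PK "will be estimated from concentration-time data using non-compartmental methods", with Cmax and Tmax among the parameters that may be assessed. No half-life is given anywhere.

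**The concern.** A non-compartmental Cmax is the highest concentration observed, and Tmax is the time of that sample. If the only early sample is drawn before the infusion ends, the peak is not observed. Recording the actual draw time does not bring it back. The error is mainly downward and depends on how each site runs the infusion and when it draws, so it adds both bias and between-site variability to Cmax, a named PK endpoint. Tmax is exposed as well: if the early sample is low enough, the 6-hour sample becomes the maximum.

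There is a related wording conflict. Section 6.3.2 places the post-dose ECG 30 minutes post-infusion, without the start-of-infusion anchor that it gives for vital signs and PK. Appendix 13.2 places the ECG 30 minutes after the start of infusion.

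**Working it through.** The plan states no figure on this point, so there is none to reproduce.

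**Inputs from the protocol.** Infusion duration T: 30 minutes nominal, 20 to 40 allowed (5.2.3). Draw time t: 30 ± 10, that is 20 to 40 minutes after the start (6.3.2, 13.2). Later sample: 6 hours ± 30 minutes, Cycles 1 and 2 only.

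**Assumptions.** Constant infusion rate; one compartment; half-life h varied from 3 hours to 12 days because the documents give none.

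**Step 1: the early sample alone.** With negligible elimination, the ratio of the sample to the end-of-infusion level is min(t/T, 1).

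| Infusion T (min) | Draw t (min) | Ratio | Shortfall |
|---|---|---|---|
| 40 | 20 | 0.50 | 50% |
| 30 | 20 | 0.67 | 33% |
| 40 | 30 | 0.75 | 25% |
| 30 | 30 | 1.00 | 0% |

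**Step 2: Cmax in Cycles 1 and 2.** Let k = ln 2 / h. During infusion C(t) = (1 − e^(−kt)) / (kT); afterwards C(t) = C(T)·e^(−k(t−T)). Observed Cmax is the higher of the early and 6-hour samples. Take T = 40 minutes, an early draw at 20 minutes, the late draw at 6.5 hours (5.83 hours after the end), and no carry-over from an earlier cycle. The late ratio is then 2^(−5.83/h), with h in hours.

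| Assumed half-life | Early ratio | Late ratio | Cmax shortfall |
|---|---|---|---|
| 3 h | 0.519 | 0.260 | 48% |
| 6 h | 0.510 | 0.510 | 49% |
| 12 h | 0.505 | 0.714 | 29% |
| 24 h | 0.502 | 0.845 | 15.5% |
| 48 h | 0.501 | 0.919 | 8% |
| 5 days | 0.500 | 0.967 | 3.3% |
| 10 days | 0.500 | 0.983 | 1.7% |
| 12 days | 0.500 | 0.986 | 1.4% |

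Other corners of the windows change little. A 30-minute infusion drawn at 20 minutes with a 24-hour half-life gives 2^(−6/24) = 0.841, or 15.9% low. From 12 hours upward the late sample is the maximum, so the recorded Tmax is about 6 hours although the modelled peak is at 40 minutes.

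**Step 3: Cycle 3 onward and retreatment.** Only the early sample is near the peak. Adding a steady-state trough from 42-day dosing, the shortfall in the 40/20 case is 46% to 50% over the same half-lives. At 12 days, for example, the trough is 0.097 of the single-dose end-of-infusion level, so the ratio is (0.500 + 0.097) / (1 + 0.097) = 0.544, or 46% low. In a first retreatment cycle the trough is near zero and the shortfall is about 50%.

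**Step 4: after the change.** A draw timed from the end of infusion has no mid-infusion shortfall for any permitted duration. Fifteen minutes of decay costs 1 − 2^(−0.25/24) = 0.7% at a 24-hour half-life and 1 − 2^(−0.25/6) = 2.8% at 6 hours.

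**The case against.** **Cmax is not read from the early sample alone.** No section says that it is. In Cycles 1 and 2, the only cycles with a post-dose profile, the 6-hour sample also counts. A reader might infer that Cmax can be 50% low throughout the trial. The documents do not support that: with a half-life of a day or more, Step 2 gives about 16% or less. This stands, with two limits. A distribution phase or a short half-life would enlarge the error, and the 6-hour sample protects Cmax only by moving Tmax.

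**Later cycles have little PK purpose.** Section 10.3.8 does not commit to Cmax or Tmax by cycle. That reduces the consequence, but the 30-minute sample is still scheduled in those cycles and the text does not exclude it from Cmax.

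**The post-infusion label forbids a mid-infusion draw.** A careful site might read it so. But for a 40-minute infusion, label and window then agree only at minute 40, and Appendix 13.2 gives the start-based time alone. The wording is ambiguous rather than permissive, which is itself reason to correct it.

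**How often this happens is unknown.** A reader might infer that half of all samples are mid-infusion. That follows by symmetry from assuming that draw time and infusion length are independent with the same continuous distribution. It says nothing about practice here, where staff may well wait for the infusion to end.

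**Little depends on it.** Escalation follows DLT counts, PK parameters are summarised descriptively, and the same windows apply at every dose, so average proportional bias need not differ between dose levels. This stands: the point concerns the accuracy of a PK endpoint, not dose-escalation decisions.

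**Conclusion.** The overlap of the two windows is certain from the text. The early sample can be 0% to 50% below the end-of-infusion level, given a constant rate and negligible elimination; the 50% needs both times at opposite extremes of their windows.

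For Cmax, the effect depends on the cycle. In Cycles 1 and 2 it is limited to about 16% at an assumed 24-hour half-life and about 3% at 5 days, in a one-compartment model, with a possible Tmax of about 6 hours as the price. From Cycle 3 and in retreatment it can reach 46% to 50%. Neither the small nor the large Cycle 1–2 figure can be asserted for this drug from the documents, because no half-life is given. The frequency of mid-infusion draws is also unknown.

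The point merits a correction to the sampling schedule. It does not show that the trial's PK results are invalid. The ECG conflict is a separate consistency matter and adds nothing to the Cmax argument.

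**What to change.** 1. In 6.3.2 and Appendix 13.2, time the first post-dose PK sample from the actual end of infusion, for example 5 to 15 minutes after it ends. The permitted infusion duration need not change.
2. Record actual infusion start, stop and draw times. Section 5.6 already requires administration to be documented in the CRF, so this may need only a check that all three times are captured.
3. Flag samples already drawn before the recorded end of infusion, and report Cmax and Tmax with and without them. Do not exclude those subject-cycles outright: that could discard a large share of the data, drop long infusions selectively, and remove Cycle 1–2 values whose Cmax error may be small.
4. Separately, reconcile the ECG timing in 6.3.2 with Appendix 13.2.

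The cost is wording in two places and the laboratory manual, plus one sensitivity summary. No sample or visit is added. The downside is that early samples taken before and after the amendment are not strictly comparable, which the report should state.
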